**Addendum Version Date: 8 APR 2022**

**APPROVAL SIGNATURES**

PPD  

08-Apr-2022 | 14:20 EDT

---

PPD Senior Principal Biostatistician, Labcorp Drug Development

PPD  

08-Apr-2022 | 14:14 EDT

---

PPD Associate Director, Biostatistics

PPD  

08-Apr-2022 | 14:25 EDT

---

PPD Director, Biostatistics

PPD  

11-Apr-2022 | 03:14 EDT

---

PPD, Medical Director

The changes to the above signed statistical analysis plan (SAP) pertaining only to summary tables (i.e., data will still be provided in listings as appropriate) are as follows, and are a result of terminating the study after the enrollment of only 10 participants:

1. Section 4: Analysis Sets: The Per Protocol Set has been removed from all analyses.
2. Section 5.1: General Considerations: Confidence intervals (CIs) will no longer be provided for any descriptive statistics.
3. Section 5.3.2: Main Analytical Approach: The exact Clopper Pearson 95% CI for the proportion of participants with effective hemostasis will no longer be provided.
4. Section 5.3.3: Sensitivity Analysis: This analysis will no longer be performed on the Per Protocol Set, but will be performed on the Efficacy Set.
5. Section 5.4.2: Main Analytical Approach: The secondary endpoint will no longer be assessed with a 2-sided 95% non-parametric CI for the median.
6. Section 5.4.3: Sensitivity Analysis: This section is removed as the analysis described in Section 5.4.2 of the statistical analysis plan will not be repeated using the Per Protocol Set.
7. Section 5.5: Exploratory Endpoint Analysis: The following exploratory efficacy endpoints will no longer be analyzed:
  - a. Relationship between intraoperative hemostasis and anti-fXa activity
  - b. Reversal of anticoagulant effect as measured by thrombin generation (TG) parameters (with endogenous thrombin potential [ETP] as the primary measure)
  - c. Occurrence of receiving 1 or more red blood cell (RBC) transfusions from start of the andexanet bolus through 12 hours after the end of surgery
  - d. The number of RBC units transfused per participant from the start of the andexanet bolus through 12 hours after the end of surgery
  - e. The use of non-RBC, non-platelet blood products and/or hemostatic agents (both system and topical) through 12 hours after the end or surgery
  - f. Observed amount of intraoperative blood loss
  - g. Difference between observed blood loss and predicted blood loss
  - h. Transfusion corrected change in hemoglobin from baseline to nadir within 12 hours after the end of surgery
  - i. Time from the signing of informed consent to the start of surgery
  - j. Time from clinical presentation at treatment facility to the start of surgery
  - k. Length of index hospitalization, assessed at the Day 30 Visit
  - l. Time from hospitalized in a post-anesthesia care unit (PACU) assessed at the Day 30 Visit
  - m. Time hospitalized in an intensive care unit (ICU), assessed at the Day 30 Visit
  - n. Length of surgery

- o. Total time in the operating room (OR)
- p. Occurrence of re-hospitalization, within 30 days of enrollment, including length of re-hospitalization (through 30 days post-enrollment)
- q. Occurrence of post-surgical major bleeding, as defined by International Society on Thrombosis and Hemostasis (ISTH) criteria, within 12 hours after the start of the initial surgery
- r. Occurrence of re-operations for bleeding, including for surgical wound hematomas, within 12 hours after the end of the initial surgery
- s. Change from baseline in tissue factor pathway inhibitor (TFPI) activity post-administration of andexanet
- t. Change from baseline in anti-IIa activity (only participants taking enoxaparin)

Removal of these endpoints also involves removal of applicable sections in the SAP (sections 5.5.1: Relationship Between Anti-fXa Activity and Hemostasis, 5.5.3: Reversal of Anticoagulant Effect – Thrombin Generation, 5.5.4: Blood Product Usage, 5.5.5: Intraoperative Blood Loss, 5.5.6: Transfusion Corrected Change in Hemoglobin, 5.5.57: Healthcare Encounter and Surgical Intervention, 5.5.8: Post-surgical Major Bleeding, 5.5.9: Tissue Factor Pathway Inhibitor (TFPI), and 5.5.10: Anti-IIa Activity.

- 8. Section 5.5.2: Anti-fXa Activity – Absolute and Percent Change from Baseline: 95% CIs will no longer be provided. Additionally, the tabulation of patients with percent reduction from baseline at time point >80% (and 95% CI) will also no longer be provided.
- 9. Section 5.6: Safety Analyses: We will no longer analyze the following:
  - a. Thrombotic Events (TEs) within 30 days of enrollment, including those suspected and confirmed by adjudication
  - b. Centrally adjudicated deaths within 30 days of enrollment, including all-cause mortality and cardiovascular mortality
  - c. Antibodies to FX, FXa, and andexanet
- 10. Section 5.6.2.2: TEAEs and SAEs by System Organ Class (SOC) and Preferred Term (PT): We will no longer provide tables summarizing treatment-emergent adverse events (TEAEs) by surgery type and baseline FXa inhibitor. Additionally, TEAEs and treatment-emergent related adverse events (AEs) will no longer be tabulated at the PT level only. Furthermore, there will no longer be a separate tabulation of TEAEs  $\geq 5\%$ .
- 11. Section 5.6.2.5: Deaths, Other SAEs, and Other Significant Adverse Events: The following will no longer be analyzed:
  - a. Events leading to death which were COVID-19 related
  - b. Survival status reported by phone on the Day 30 or End of Study visit
  - c. Deaths assessed by the event adjudicating committee (EAC)
  - d. Deaths through the 30 Day Follow-up Visit by reason for death (Cardiovascular, non-cardiovascular)

12. Section 5.6.2.6: Adverse Events of Special Interest (AESIs): These analyses are to be removed.
13. Section 5.6.4: Vital Signs and Weight: The number of participants having clinically significant vital signs at each visit will no-longer be tabulated.
14. Section 5.7.2: Subgroup Analyses: Subgroup analyses will no-longer be performed.
15. Section 6.2.1: Protocol Deviations: Protocol deviations will no-longer be tabulated.
16. Section 6.2.2: Demographics, Baseline Characteristics, and History: Baseline and demographic characteristics will no-longer be summarized for the Efficacy Set. Additionally, COVID-19 diagnosis will no-longer be summarized for the Safety Set.
17. Section 6.2.3: Medical/Surgical History and Baseline Physical Examination: Baseline physical examination will not be tabulated.
18. Section 6.2.5: COVID-19 Impact: The number of participants with any number of visits missed or modified due to exposure to, or diagnosis of COVID-19 will no-longer be tabulated.

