## **2. STATISTICAL HYPOTHESES**

No hypothesis testing will be conducted in this single-arm, proof-of-concept study.

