#### 5.3.2. Main Analytical Approach

The number of participants achieving effective hemostasis will be tabulated. An exact Clopper-Pearson 95% CI for the proportion of participants with effective hemostasis will be provided.

All participants in the Efficacy Set will be included in the primary analysis except for certain EAC adjudicated cases as described below.

Cases where it is determined that there is insufficient information, or where it is not otherwise possible to properly assess the effect of treatment, will be classified by the EAC as 'non-evaluable due to administrative reasons' (eg, participant transferred to another facility for administrative purposes) or 'non-evaluable due to clinical reasons' (eg, participant died).

Participants whose hemostatic efficacy is 'non-evaluable due to administrative reasons' will be excluded in all applicable efficacy analyses.

Participants whose hemostatic efficacy is 'non-evaluable due to clinical reasons' will be considered as having moderate/poor hemostatic efficacy and included in the denominator in the primary analysis as having ineffective hemostasis; but treated as not having an effective hemostasis value and thus excluded in the denominator in a sensitivity analysis (Section 5.3.3).

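### The addendum drops the exact 95% confidence interval for the primary proportion because only 10 participants were enrolled, although it is the only planned statement of uncertainty for that estimate and is valid at small n

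*SAP*

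**What the plan says.** SAP v1.0, Section 5.3.2, tabulates the number of participants with effective hemostasis and adds: "An exact Clopper-Pearson 95% CI for the proportion of participants with effective hemostasis will be provided". Table 1 names the proportion as the summary measure. Section 2 states: "No hypothesis testing will be conducted in this single-arm, proof-of-concept study". Section 3 justifies about 100 enrolled (80 after 20% attrition) only by a 95% interval half-width below 11%.

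The addendum of 8 Apr 2022 says that its changes "are a result of terminating the study after the enrollment of only 10 participants". On intervals it makes these changes:

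- Item 2 (Section 5.1): "Confidence intervals (CIs) will no longer be provided for any descriptive statistics".
- Item 3 (Section 5.3.2): "The exact Clopper Pearson 95% CI for the proportion of participants with effective hemostasis will no longer be provided".
- Item 5 (Section 5.4.2): "The secondary endpoint will no longer be assessed with a 2-sided 95% non-parametric CI for the median".
- Item 8 (Section 5.5.2, anti-fXa activity): "95% CIs will no longer be provided".

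The changes are described as "pertaining only to summary tables (i.e., data will still be provided in listings as appropriate"). The addendum does not touch the sentence in Section 5.3.2 that requires the count. Item 4 keeps the sensitivity analysis on the Efficacy Set. Nothing is put in the place of the interval for the primary proportion.

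**The concern.** A single-arm study without a hypothesis test delivers an estimate and its precision. Here precision was also the whole basis of the sample size. Once the interval is removed, the primary result is a count and a percentage from at most 10 people, and the summary tables do not say how far the true proportion could lie from that percentage.

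The stated reason does not support the deletion. Small numbers do undermine the normal-approximation interval that Section 5.1 sets as the default for binary variables. Section 5.3.2 had already replaced that default, for this endpoint, with an exact method that does not depend on a large sample. The interval is widest, and so tells the reader most, when the sample is small.

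**Working it through.** **Inputs.** Planned evaluable n = 80, attrition 20% and half-width below 11% (SAP Section 3). Two-sided 95% level (Section 5.1). Enrolled: 10 (addendum), which is an upper bound for the Efficacy Set, because Section 4 also requires treatment, surgery and a baseline anti-fXa activity at or above the threshold. Section 5.3.2 further excludes administratively non-evaluable cases from the denominator. The size of the Efficacy Set and the observed count x are not in the documents, so the values of x and n below are assumptions.

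**1. The plan's own figure.** Normal approximation at the worst case p = 0.5: 1.96 × √(0.25/80) = 0.1096, or 10.96%, which is below 11%. Enrolment: 80/(1 − 0.20) = 100. Both reproduce. The exact interval at n = 80 is slightly wider, with a largest half-width of 11.40 points at 40/80.

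**2. Exact interval at the sizes now possible.** The lower limit is the 0.025 quantile of Beta(x, n − x + 1). The upper limit is the 0.975 quantile of Beta(x + 1, n − x). When x = n, the lower limit reduces to 0.025^(1/n) and the upper limit is 1.

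- 10/10: 0.025^(1/10) = 0.692, so 69.2% to 100%.
- 8/8: 0.025^(1/8) = 0.631, so 63.1% to 100%.

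| Assumed x/n | Proportion | Exact 95% CI |
|---|---|---|
| 10/10 | 100% | 69.2% to 100% |
| 9/10 | 90% | 55.5% to 99.7% |
| 8/10 | 80% | 44.4% to 97.5% |
| 5/10 | 50% | 18.7% to 81.3% |
| 8/8 | 100% | 63.1% to 100% |
| 7/8 | 87.5% | 47.3% to 99.7% |

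At n = 10 the half-width runs from 15.4 points (0/10 or 10/10) to 31.3 points (5/10). The latter is about 2.7 times the exact maximum at n = 80 (31.3/11.4).

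**3. Why the method matters.** The normal-approximation half-width is 1.96 × √(p(1 − p)/n). At 10/10 this is 0, so that interval would claim perfect precision. The exact interval does not fail in this way.

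**4. The secondary median.** The order-statistic interval from rank k to rank n − k + 1 covers the median with probability 1 − 2 × Σ C(n, i)/2^n, summed over i = 0 to k − 1.

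- n = 10, ranks 2 to 9: 1 − 2(1 + 10)/1024 = 97.9%.
- n = 8, ranks 2 to 7: 1 − 2(1 + 8)/256 = 93.0%, too low. Ranks 1 to 8 give 99.2%.
- n = 7, ranks 2 to 6: 1 − 2(1 + 7)/128 = 87.5%, too low. Ranks 1 to 7 give 98.4%.
- n = 6, ranks 2 to 5: 1 − 2(1 + 6)/64 = 78.1%, too low. Ranks 1 to 6 give 96.9%.
- n = 5, ranks 1 to 5: 1 − 2/32 = 93.75%, so no 95% interval exists.

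At n = 6 to 8 the 95% interval is therefore the minimum to the maximum, and Section 5.1 already reports both.

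**The case against.** The removal is deliberate, dated and signed, with its reason stated, and the plan remains consistent with itself. The addendum does not say that an exact interval is invalid at small n. Cutting a study stopped at 10 of about 100 planned participants back to descriptive reporting is a recognisable choice. Little is lost either, because an exact binomial interval is fully determined by the count and the denominator, both of which stay in the output. A count out of at most 10 already warns the reader.

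All of that stands, and it limits the severity. It does not make the deletion sound: a pre-specified part of the primary result should not be left for readers to rebuild, and a wide interval labelled descriptive is itself descriptive reporting.

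Three stronger readings are tempting, and the document does not support them:

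- A reader might infer that the missing interval hides a failure to rule out unacceptable hemostasis rates. The SAP sets no performance goal, null value or threshold, so no rate is defined as unacceptable.
- A reader might infer that the secondary endpoint suffers equally. It does not. Section 5.1 keeps the quartiles, minimum and maximum, and at n = 6 to 8 the interval would add no new numbers.
- A reader might infer that ready-made programs only need to be switched back on. SAP v1.0 specifies the method, but Section 6.4 leaves guidance code to a separate data presentation plan, so this cannot be known.

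**Conclusion.** The point holds for the primary endpoint, as a reporting weakness of moderate weight. Items 2 and 3 together remove the only planned statement of uncertainty for the primary proportion, for a reason (few participants) that does not count against an exact interval. It does not reach the level of a defect that must be corrected before any result can be used: no decision rule or test depends on the interval, and it can be recomputed from retained output.

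The size of the effect is conditional. If all of 10 evaluable participants had effective hemostasis, the interval would still reach down to 69.2%; with 8 of 8, to 63.1%; with 9 of 10, to 55.5%. These are illustrations under assumed counts, not results. Restoring the interval does not recover the planned precision; it shows how much was lost.

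**What to change.** Delete addendum item 3 and add to item 2 an exemption for the primary endpoint. In the primary table, report n/N, the proportion and the exact Clopper-Pearson two-sided 95% interval, labelled descriptive. Keep the exact method named, so that the normal-approximation default of Section 5.1 does not apply. State whether the retained sensitivity analysis, which repeats the primary one, carries the same interval.

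Optionally, withdraw item 5 as well and give the order-statistic interval for the median with its attained coverage, or the range alone if n is below 6.

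The cost is a change to the addendum wording and one added interval in the primary table. It needs no new data, and the calculation uses only the count and the denominator.

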## VERSION HISTORY

This Statistical Analysis Plan (SAP) for Study 19-515 is based on Protocol Amendment 2, dated 20 Jul 2020.

SAP Version	Version Date	Change	Rationale
1.0	24 SEP 2021	Not applicable	Original version

## 1. INTRODUCTION

This Statistical Analysis Plan describes the final statistical methods for analyzing efficacy and safety data for Protocol “Prospective, Open-label Study of Andexanet Alfa in Patients Receiving a Factor Xa Inhibitor who Require Urgent Surgery (ANNEXA-S)”. Standard data presentation instructions, and table, figure, and listing specifications are contained in the Data Presentation Plan (DPP) in a separate document.

### 1.1. Objectives and Endpoints

The overall objective of the study is to gain direct insights regarding the efficacy and safety of andexanet in Factor Xa (FXa)-anticoagulated participants requiring urgent surgery. Additional information obtained from this study will include the adequacy and duration of andexanet dosing.

The attributes of the estimands (treatment, population, variable, intercurrent event, and summary measure) corresponding to the primary and secondary efficacy endpoints are summarized in Table 1 as follows:

**Table 1: Objectives, Endpoints, and Estimand Attributes**

Objective	Endpoints and Corresponding Estimand Attributes
Primary	

 
To evaluate hemostatic efficacy following andexanet alfa treatment
 
	Primary endpoint: Achievement of effective hemostasis (binary outcome) 
 
Treatment: Andexanet
 
Population: Efficacy Set
 
Variable: Hemostasis (Effective/Ineffective)                             
 
Effective: intraoperative hemostasis = excellent/good
 
Ineffective: intraoperative hemostasis = moderate/poor
 
 
 
Intercurrent Events:                             
 
Participants whose hemostatic efficacy is ‘non-evaluable due to clinical reasons’ (according to the Endpoint Adjudication Committee [EAC] charter and adjudicated as such by the EAC) will be treated as ineffective hemostasis
 
Participants whose hemostatic efficacy is ‘non-evaluable due to administrative reasons’ (according to the EAC charter and adjudicated as such by the EAC) will be treated as not having an effective hemostasis value
 
 
 
Summary Measure: Proportion of patients achieving effective hemostasis
 

Secondary	

 
To evaluate the effect of andexanet on anti-fXa activity
 
	Secondary endpoint: Percent change in anti-fXa activity from baseline to evaluation period nadir 
 
Treatment: Andexanet
 
Population: Efficacy Set
 
Variable: Percent change in anti-fXa activity from baseline to the nadir for the evaluation period from the end of the andexanet bolus to the end of the andexanet infusion
 

Objective	Endpoints and Corresponding Estimand Attributes
	
 
• Intercurrent Event: Missing on-treatment nadir value will be treated as 0% change from baseline in anti-fXa activity
 
• Summary Measure: Median percent change in anti-fXa activity from baseline to on-treatment nadir
 

Other endpoints are described in Section 5.5.

## 1.2. Study Design

This is a Phase 2 multicenter, prospective, open-label, proof-of-concept study of andexanet alfa (referred to subsequently as “andexanet”), with the objectives of determining the efficacy and safety of andexanet in participants who require urgent surgery (must occur within 12 hours of consent) who have, within 15 hours prior to surgery, received 1 of the following FXa inhibitors: apixaban, rivaroxaban, edoxaban, or enoxaparin. Approximately 100 participants will be enrolled. The duration of the study for any individual participant will be up to 37 days.

The start of surgery must be within 15 hours following the last dose of FXa inhibitor. If the time from last dose of FXa inhibitor is unknown or greater than 15 hours, participants with a local laboratory anti-fXa activity level obtained within 2 hours prior to consent  $> 100$  ng/mL ( $> 0.5$  IU/mL for participants taking enoxaparin) may be enrolled. Participants enrolled in this manner should receive a high-andexanet dosing regimen. In such cases, the start of surgery must begin no greater than 4 hours after the blood collection for the local test. The prespecified time periods and/or anti-fXa activity levels are designed to ensure participants have sufficiently high anti-fXa activity levels.

Participants will receive 1 of 2 dosing regimens of andexanet based on which FXa inhibitor they received and the dose and timing of the most recent dose of FXa inhibitor. Participants will receive an intravenous (IV) bolus of andexanet administered over approximately 15 to 30 minutes (depending on dose), followed immediately by an IV continuous infusion of andexanet for 2 hours, irrespective of the duration of surgery. The bolus must be completed immediately prior to the start of surgery (ie, at the first incision; designated as Time 0). The infusion should continue from prior to the start of surgery (initial skin incision) until the end of surgery (close of skin incision, or, if skin closure is not completed by intention, an equivalent milestone such as, dressing or packing the surgical incision). If the end of surgery occurs prior to completion of the initial 2-hour infusion, the infusion should continue into the postoperative period until it is completed (120 minutes). Additional andexanet, be it for extended treatment or re-dosing, may be given at the discretion of the Investigator when specific criteria regarding duration of surgery and/or postoperative complications are met (see Protocol Section 6.2).

The primary efficacy endpoint is the achievement of hemostatic efficacy, as determined by the investigator’s assessment of intraoperative hemostasis using a pre-specified 4-point scale and confirmed by adjudication by an independent Endpoint Adjudication Committee (EAC) (Section 5.3.1).

In addition to hemostatic efficacy, the EAC will adjudicate all deaths, thrombotic events (TEs), and post-surgical major bleeding events (eg, surgical hematomas). The EAC will be blinded to all anti-fXa levels. An independent Data Safety Monitoring Board (DSMB) will review study

data once the 30-day visit is completed for the participant recruitment of approximately 33 and 66 participants.

All adverse events (AEs), including serious adverse events (SAEs), and survival will be followed through the Day 30 Post-treatment Visit.

See Section 6.7 for Schedule of Events and the protocol for additional details.

## **2. STATISTICAL HYPOTHESES**

No hypothesis testing will be conducted in this single-arm, proof-of-concept study.

### **3. SAMPLE SIZE DETERMINATION**

Approximately 100 participants will be enrolled. After accounting for 20% attrition (eg, canceled surgeries, discontinued and/or non-evaluable participants, or baseline anti-fXa activity analyzed by central laboratory less than the evaluability threshold), a sample size of 80 participants will provide an estimate of the proportion of achieving effective (excellent or good) hemostasis with a margin of error (half width of the 95% confidence interval [CI]) that is less than 11%.

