## 5. STATISTICAL ANALYSES

### 5.1. General Considerations

For continuous variables, the number of observations, mean, median, standard deviation, first quartile (Q1), third quartile (Q3), interquartile range (IQR), and minimum and maximum values, will be presented. For categorical variables, unless specified otherwise, counts and percentages will be based upon number of participants with non-missing values in the analysis set.

Confidence intervals will be provided for the mean for all continuous efficacy variables except for percent change from baseline variables, for which CIs for the median will be generated. For binary variables, normal-approximated CIs for the binomial proportion will be provided unless stated otherwise.

No hypothesis testing will be conducted in this single-arm, proof-of-concept study. All CIs will be 2-sided and reported at the 95% confidence level unless stated otherwise.

Summary statistics will be provided for each time point/visit at which the variable is collected unless otherwise stated. Visit/time point windows will not be employed. See Section 6.7 for the schedule of study activities.

Summary table(s) will be generated for all data described in this SAP unless otherwise noted. At a minimum, data listings will be provided for these data.

In general, no missing data imputation will be performed unless stated otherwise.

It is anticipated that statistical summaries will be performed using Statistical Analysis Software (SAS®) Version 9.4 (SAS Institute, Inc., Cary, NC, USA) or higher. Additional software may be used for the production of graphics and for statistical methodology not available in SAS.

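### Section 3's unconditional half-width below 11% with 80 participants holds for a normal-approximation interval but not, at mid-range rates, for the exact Clopper-Pearson interval set in Section 5.3.2 (up to 11.4%)

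*SAP*

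**What the plan says.** Section 3 (Sample Size Determination) sets the enrolment target: "Approximately 100 participants will be enrolled". It then reduces that number for losses ("After accounting for 20% attrition") and bases the precision claim on those who remain: "a sample size of 80 participants will provide an estimate of the proportion of achieving effective (excellent or good) hemostasis". The precision promised for that estimate is worded as "with a margin of error (half width of the 95% confidence interval [CI]) that is less than 11" per cent. No anticipated rate of effective hemostasis and no method of interval construction is given there.

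Section 5.1 (General Considerations) sets a default: "For binary variables, normal-approximated CIs for the binomial proportion will be provided unless stated otherwise". It also fixes the level: "All CIs will be 2-sided and reported at the 95% confidence level unless stated otherwise".

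Section 5.3.2 (Main Analytical Approach) departs from that default for the primary endpoint: "An exact Clopper-Pearson 95% CI for the proportion of participants with effective hemostasis will be provided".

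The addendum of 8 April 2022, written after the study was terminated with 10 participants enrolled, withdraws this interval in its item 3: "The exact Clopper Pearson 95% CI for the proportion of participants with effective hemostasis will no longer be provided". The addendum confines itself to summary tables and lists no change to Section 3.

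**The concern.** Section 2 rules out hypothesis testing, so the precision statement in Section 3 is the only quantitative justification of the sample size in this document. Because it carries no condition on the observed rate, a reader will take it as a worst-case guarantee. Such a guarantee depends on the interval method when the margin is tight, and here the two sections do not match. The primary endpoint is an explicit exception to the normal-approximation default, and the exact interval is wider. Anyone quoting Section 3 as the planned precision would be quoting a bound that the planned interval does not guarantee.

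**Working it through.** **Inputs.** Enrolment of 100, attrition of 20%, 80 participants for the estimate and a claimed half-width below 11% (all Section 3). Two-sided 95% level (Section 5.1). Exact Clopper-Pearson interval (Section 5.3.2). The expected proportion is not given anywhere in the document, so the whole range from 0/80 to 80/80 was examined, with 50% as the worst case.

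**Step 1: attrition.** 100 × (1 − 0.20) = 80. The plan's number reproduces.

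**Step 2: the plan's half-width.** Under the normal approximation the half-width is 1.96 × √(p(1 − p)/n), which is largest at p = 0.5:

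1.96 × √(0.25/80) = 1.96 × 0.0559 = 0.1096, or 10.96%.

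This lies 0.04 points under 11%, so the claim holds at every proportion for this method. That it is the source of the figure is an inference, since Section 3 does not say.

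**Step 3: the prescribed interval.** For x successes in n, the Clopper-Pearson limits are

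- lower = 2.5% quantile of Beta(x, n − x + 1)
- upper = 97.5% quantile of Beta(x + 1, n − x)

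and the half-width is (upper − lower)/2. At x = 40, n = 80 the limits are 38.6% and 61.4%, so the half-width is (61.4 − 38.6)/2 = 11.4%.

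| Observed | Rate | Exact half-width | Normal approximation |
|---|---|---|---|
| 40/80 | 50% | 11.40% | 10.96% |
| 48/80 | 60% | 11.18% | 10.74% |
| 50/80 | 62.5% | 11.06% | 10.61% |
| 51/80 | 63.75% | 10.99% | 10.53% |
| 56/80 | 70% | 10.51% | 10.04% |
| 64/80 | 80% | 9.28% | 8.77% |
| 72/80 | 90% | 7.17% | 6.57% |

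The exact half-width is symmetric about 50%. Over all counts from 0 to 80 it is at or above 11% for 30 to 50 successes (37.5% to 62.5%) and below 11% for every other count.

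**Step 4: how often that band would arise.** With 80 analysed, the probability of a count from 30 to 50 is 98% if the true rate is 50%, 71% at 60%, 9% at 70% and 0.02% at 80%. These true rates are assumptions that show the range.

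**Step 5: what an unconditional exact bound would take.** The maximum Clopper-Pearson half-width is 11.05% at n = 85 and 10.98% at n = 86. So 86 is the smallest number that stays below 11% at every rate. With 20% attrition, 86/0.8 = 107.5, or 108 enrolled.

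**The case against.** The strongest reply is that nothing now depends on this figure. The stated number reproduces under the method that Section 5.1 makes the default, so it is not a slip of calculation. The excess is at most 0.4 points and occurs only in the middle of the range. The target of about 100 and the round 20% attrition are themselves looser than that. No decision uses the 11%: there is no hypothesis test (Section 2), no interim efficacy analysis (Section 5.8) and no success criterion. The addendum removed the interval from the summary tables. Its silence on Section 3 is no fault, because it deals only with summary tables.

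All of this stands as a limit on weight. It does not remove the mismatch. Section 5.1 applies its default only where nothing else is stated, and Section 5.3.2 states something else for this proportion. The document gives no expected rate that would place the result outside the middle band, although it gives none that would place it inside either.

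Stronger readings are tempting but not supported:

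- **The trial was undersized.** A reader might infer this from the 86 in the working. It would follow only if a bound below 11% at every rate were a requirement, and the SAP sets no such requirement.
- **The interval method should be switched.** The Wilson interval has a half-width of 10.70% at 40/80 and would fit the claim. But adopting it would change a prespecified method to suit a planning figure, for an interval since withdrawn.
- **The bound fails more widely.** Measured by the longer arm of the asymmetric exact interval, 11% is reached for 21 to 59 of 80. Section 3, however, defines its margin as the half-width.
- **Precision can be restated for the 10 enrolled.** The primary analysis uses the Efficacy Set, which requires treatment, surgery and a baseline anti-fXa level at or above threshold (Section 4). Its size is not given and may be below 10.

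**Conclusion.** The point holds as a minor correction to the planning text of SAP v1.0. Read as the unconditional bound it is, the Section 3 statement is true for the normal approximation (10.96% at worst) and untrue for the exact interval prescribed in Section 5.3.2 (11.4% at worst, above 11% from 37.5% to 62.5% observed). Outside that range the exact interval meets the stated figure.

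The conclusion rests on two assumptions: that exactly 80 participants enter the denominator, as Section 3 plans, and that the statement is meant to hold at any rate, since no rate is named. If a high rate had been assumed and stated, such as 80%, the exact half-width would be 9.3% and the claim would be correct.

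The design, the conduct and the reported results are unaffected.

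**What to change.** Replace the precision clause in Section 3 with: *half-width of the exact Clopper-Pearson 95% CI at most 11.4% (worst case, observed 50%); 9.3% at 80%*. This names the method, agrees with Section 5.3.2 and gives the condition under which each figure applies. If the SAP is not reopened, the same sentence can go in the clinical study report where the planned sample size is described.

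The cost is one sentence and a slightly less favourable planning figure. The sample size, the prespecified interval method and the addendum stay as they are.
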